9.3. Special Considerations

9.3.1. Adverse Events of Special Interest

and patients should be closely monitored should these AEs occur.

These events will be followed closely during the study and considered AESIs.

9.3.1.1. Potential for Adrenal Suppression

Transient cortisol reduction is a well described physiologic response in patients who receive IA cortisol injections and should not necessarily be considered an AE. Laboratory evidence of adrenal insufficiency should be assessed in conjunction with clinical signs and symptoms.

Patients and investigators will be educated about symptoms of adrenal insufficiency, and an assessment of clinical signs and symptoms indicating potential adrenal insufficiency will be performed as part of AE evaluation at every visit or contact.

Patients will be provided a wallet card identifying the potential risk for adrenal insufficiency and asked to carry it at all times. This card should include the patient's identifying information, contact information for the investigator, and should note the potential need for emergency glucocorticoid therapy in the setting of shock, surgery, etc.

Morning serum cortisol as measured by the central laboratory will be blinded to the patient, site staff, and blinded study team members (except Screening, Day 1 [pre-dose], and Week 20); results will be reviewed by a separate unblinded medical monitor.

If there is clinical evidence of adrenal insufficiency that may compromise the patient's safety, the investigator should use a local laboratory to obtain a cortisol level or

and/or refer the patient to his or her primary care physician or to an endocrinologist. The investigator may also contact the blinded medical monitor to discuss the patient's case and request review of prior cortisol values.

The unblinded medical monitor will monitor all serum cortisol values. If sustained cortisol suppression is observed beyond 4 weeks following an injection, or any other cortisol values are seen that might appear to compromise patient safety, the unblinded medical monitor may contact

the investigator to review the patient's condition including any potential signs or symptoms of adrenal insufficiency and discuss potential follow-up laboratory testing.

9.3.2. Pregnancy

All women of childbearing potential who participate in the study should be counseled on the need to practice adequate birth control and on the importance of avoiding pregnancy during study participation.

Women of childbearing potential must use a highly effective method of birth control until at least 6 months after the last dose of study drug. Acceptable and effective methods of birth control for this study include:

- Absolute sexual abstinence (no sexual intercourse or genital contact with a male partner)
- Monogamous partner who is vasectomized
- Use of double-barrier contraception
- Use of an approved insertable, injectable, transdermal, or combination oral contraceptive for greater than 2 months prior to Screening.

Pregnancy testing will be conducted before administration of the study drug on every woman of childbearing potential. A woman who is found to be pregnant at Screening will be excluded from the study and considered to be a screening failure.

After participation in the study, women should be asked to contact the investigator or study staff immediately if pregnancy occurs or is suspected. The investigator is responsible for following the pregnancy until delivery or termination.

10. DATA SAFETY MONITORING BOARD

A data safety monitoring board will not be used in this study.

11. STATISTICS

11.1. Study Endpoints

11.1.1. Efficacy Endpoints

11.1.1.1. Primary Efficacy Endpoint

The primary efficacy endpoint is:

[figure not shown]
- Change from Baseline in WOMAC Pain at Week 12 (Group A vs. Group C)

11.1.1.2. Secondary Efficacy Endpoints

The following key secondary efficacy endpoints will be evaluated in a hierarchical sequence:

[figure not shown]
1. Change from Baseline in WOMAC Pain at Week 16 (Group A vs. Group C)
2. Change from Baseline in WOMAC Pain at Week 20 (Group A vs. Group C)
3. Change from Baseline in WOMAC Pain at Week 24 (Group A vs. Group C)
4. Change from Baseline in WOMAC Pain at Week 36 (Group A vs. Group C)
5. Change from Baseline in WOMAC Function at Week 12 (Group A vs. Group C)
6. PGIC at Week 12 (Group A vs. Group C)
7. Total rescue acetaminophen consumption through Week 12 (Group A vs. Group C)
8. Durable responder with $\geq 30\%$ decrease in WOMAC Pain from Baseline for Weeks 4 through 12 (Group A vs. Group C)
9. Change from Baseline in WOMAC Function at Week 36 (Group A vs. Group C)
10. PGIC at Week 36 (Group A vs. Group C)
11. Change from Baseline in WOMAC Pain at Week 12 (Group A vs. Group B)
12. Change from Baseline in WOMAC Pain at Week 52 (Group A vs. Group C)

11.1.2. Additional Endpoints

- Absolute value, change, and percent change from Injection 1 Baseline at each week in average daily pain in the index knee
- Total and average daily consumption of rescue acetaminophen by week

11.2. Analysis Populations

The following analysis populations are planned for this study:

Safety Population (SAF): The Safety Population includes all patients who receive any dose of study drug; the population will be determined for each study period. Injection 1 Period reporting will require that Injection 1 has been received; Injection 2 Period reporting will require that Injection 2 has been received. The SAF population will be the primary population for safety evaluation.

Full Analysis Set (FAS): The FAS includes all randomized patients who receive Injection 1. The FAS population will be the primary population for efficacy analysis, as well as for descriptive summaries other than safety (demographic and baseline, disposition, protocol deviation, medical history, etc.).

Per Protocol Population (PP): The PP Population includes all patients who receive 2 doses of study drug, have primary efficacy evaluation at Weeks 12, 24, and 36, and do not have important protocol deviations affecting primary efficacy evaluation.

Modified Per Protocol (mPP): The mPP Population includes all patients who receive the first dose of study drug, have primary efficacy evaluation at Weeks 12 and 24, and do not have important protocol deviations affecting primary efficacy evaluation.

The **PP** and **mPP** populations will be used for supportive analysis of selected efficacy endpoints. For the PP population, patients must have a valid WOMAC Pain assessment at Baseline, Week 12, Week 24, and Week 36; for the mPP population, patients must have a valid WOMAC Pain assessment at Baseline, Week 12, and Week 24. (A valid assessment is within the analysis visit window and not excluded due to an intercurrent event as described in Section 11.3.3.1).

Important protocol deviations are determined in accordance with the protocol deviation guidance plan. Membership in the PP and mPP analysis populations will be determined after blinded data review of important protocol deviations affecting primary efficacy evaluation before database lock and study unblinding.

If a patient is randomized incorrectly or is administered the incorrect study drug, analyses of the FAS population will be based on the assigned treatment, whereas analyses of all other populations will be based on the actual treatment received.

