VISIT STRUCTURE: There will be up to 19 study visits, including Screening (Visit 1), Baseline (Day 1/Visit 2), Week 1 (Visit 3), Week 2 (Visit 4), and 6 visits occurring every 4 weeks from Week 4 (Visit 5) through Week 24 (Visit 10), Week 25 (Visit 11), Week 26 (Visit 12), and every 4 weeks from Week 28 (Visit 13) through Week 52 (Visit 19). Week 25 (Visit 11) and Week 26 (Visit 12) will only be required for patients who receive Injection 2 at Week 24 (Visit 10).

STUDY DURATION: Duration of patient participation will be up to 56 weeks, including a Screening period of up to 4 weeks before randomization, Injection 1 Period of 24 weeks and Injection 2 Period of 28 weeks.

STUDY POPULATION

This study will randomize approximately 500 patients, according to the following inclusion and exclusion criteria:

Inclusion Criteria:

1. Male or female ≥ 40 years of age, inclusive.
2. Body mass index $\leq 40 \text{ kg/m}^2$.
3. Has symptoms associated with OA of the index knee for at least 6 months before Screening.
4. Documented diagnosis of OA in the index knee based on American College of Rheumatology Criteria for Classification of Idiopathic OA of the knee (clinical and radiological including standing fixed-flexion posterior-anterior X-ray of the knee).
5. OA with Kellgren-Lawrence Grade 2 to 3 severity in the index knee based on the grade per X-ray assessed by a central radiologist reader at Screening.
6. Initial patient-reported pain with NRS score ≥ 4 (on a 0-10 scale) in at least 1 knee (index knee) at Screening (rating of average pain over the previous 24 hours).
7. Patient-reported pain with average daily NRS score of 5.0 to 9.0 (inclusive) in the index knee, AND with non-index knee pain score of ≤ 4.0 , based on diaries completed daily for at least 5 of the last 7 days of the screening period before randomization.
8. Patient-reported WOMAC Pain sub-scale (hereafter referred to as WOMAC Pain) score ≥ 6 (combined score on a 0-20 scale) in the index knee before dosing at Baseline.
9. a. IF FEMALE, must meet all of the following:
 - Not breast feeding;
 - Not planning to become pregnant during the study;

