6. STUDY DESIGN

6.1. Overall Study Design and Plan

This is a Phase 3 randomized, double-blind, placebo- and active comparator-controlled pivotal study. Approximately 500 adult patients with moderate to severe pain due to OA of the knee who meet all entry criteria will be enrolled and randomized into a 2:1:1 ratio to receive TLC599 12 mg (Group A), DSP 4 mg (Group B), or Placebo (normal saline) (Group C) via IA injection into the designated index knee at Baseline (Injection 1). At Week 24, patients will receive Injection 2 per their randomly assigned dosing regimen (Group A, B, or C) via IA injection into the index knee (see Section 6.6.3 for Criteria for Injection 2). Patients who received TLC599 12 mg (Group A) or DSP (Group B) for Injection 1 will receive blinded TLC599 12 mg for Injection 2 and those who received Placebo for Injection 1 (Group C) will receive Placebo for Injection 2.

All patients will be followed for a total of 52 weeks, regardless of whether or not they receive Injection 2. Patients who do not receive Injection 2 will be encouraged to continue in the study through 52 weeks of follow-up. Efficacy and safety of 2 doses of TLC599 will be evaluated in comparison with Placebo and DSP through Week 52.

To enter the study, patients must be at least 40 years of age and have documented diagnosis of OA in the index knee based on American College of Rheumatology (ACR) Criteria for Classification of Idiopathic OA of the knee (the ACR diagnostic criteria is provided in Appendix A). Patients will not be eligible if they have unstable index knee joint as determined by the investigator based on physical examination (with or without buckling or giving way) because of an acute injury (defined as injury within 6 months, e.g., anterior cruciate ligament injury or tear).

The study duration is expected to be up to 56 weeks for each patient, including a Screening period of up to 4 weeks before randomization, Injection 1 Period of 24 weeks and Injection 2 Period of 28 weeks.

Patients will return to the study site at Week 1, Week 2, and every 4 weeks through Week 52 post-dose to complete efficacy and safety assessments as applicable. Patients who receive Injection 2 will return to the clinic for 2 additional follow-up visits (Week 25 and Week 26).

Efficacy will be assessed by WOMAC, numeric rating scale (NRS), [REDACTED] and Patient Global Impression of Change (PGIC) at the time points indicated in the schedule of events (Section 1.1).

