8.2. Study Duration

The planned sequence and maximum duration of the study periods for each patient will be as follows:

1. Screening period: up to 4 weeks
2. Injection 1 period: up to 24 weeks following the administration of Injection 1
3. Injection 2 period: up to 28 weeks following the administration of Injection 2

Patients who do not receive Injection 2 will be followed for up to 52 weeks following the administration of Injection 1.

The maximum study duration for each patient is approximately up to 56 weeks.

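### Do safety data collected after Week 24 from patients who never receive Injection 2 fall outside every safety summary?

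*Combined protocol and SAP*

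**What the plan says.** Section 11.2 defines the Safety Population as everyone given any dose and adds that "the population will be determined for each study period". The entry rule is "Injection 1 Period reporting will require that Injection 1 has been received; Injection 2 Period reporting will require that Injection 2 has been received".

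The period lengths are given in the synopsis ("Injection 1 Period of 24 weeks and Injection 2 Period of 28 weeks"), again in Section 6.1, and in Section 8.2. Section 8.2 opens with "The planned sequence and maximum duration of the study periods for each patient will be as follows" and lists "Injection 1 period: up to 24 weeks following the administration of Injection 1" and "Injection 2 period: up to 28 weeks following the administration of Injection 2". It then has a separate line for the patients at issue: "Patients who do not receive Injection 2 will be followed for up to 52 weeks following the administration of Injection 1". Section 6.1 agrees: "All patients will be followed for a total of 52 weeks, regardless of whether or not they receive Injection 2". The schedule in Section 1.1 places the visits after Week 24 under the Injection 2 Period heading.

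Section 11.3.4 summarises safety data descriptively by group within each injection period. It names two comparisons, one of which is Group A after Injection 1 against Group A after Injection 2. The synopsis says that all data are listed as well as summarised.

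**The concern.** Take a patient who has Injection 1, does not have Injection 2 and stays to Week 52. After Week 24 this patient is past the stated length of the first period and fails the entry condition for the second. If safety is tabulated only within periods, the patient's later data would be collected and listed but would enter no summary table.

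This could matter because single-dose safety is a secondary objective (Section 5.2), and only these patients can be observed for up to 52 weeks after one injection. They are also partly selected on safety, since adrenal insufficiency through Week 24 is one of the visible reasons in Section 6.6.3 for not giving Injection 2. Leaving out their later course could hide how such events evolve.

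**Working it through.** **The plan's own durations.** Section 8.2: 4 (Screening) + 24 (Injection 1) + 28 (Injection 2) = 56 weeks, the stated maximum. After Injection 1: 24 + 28 = 52 weeks. Both agree with the text.

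**What one Injection-1-only patient contributes after Week 24** (schedule in Section 1.1 and visit lists in Section 8.3; Weeks 25 and 26 are not required of these patients):

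| Item | Through Week 24 | After Week 24 | Share after |
|---|---|---|---|
| Follow-up weeks | 24 | 28 | 28/52 = 54% |
| Cortisol samples | 8 (Weeks 1, 2, 4, 8, 12, 16, 20, 24) | 7 (Weeks 28, 32, 36, 40, 44, 48, 52) | 7/15 = 47% |
| Chemistry, hematology and HbA1c | 2 (Weeks 12, 24) | 3 (Weeks 36, 48, 52) | 3/5 |
| ECG | 1 (Week 24) | 2 (Weeks 48, 52) | 2/3 |
| Knee radiograph | 1 (Week 24) | 1 (Week 52) | 1/2 |

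**How much follow-up in total.** The documents do not say how many patients will miss Injection 2, so the share p is an assumption. The upper bound in patient-years is N × p × 28/52.

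- All arms, N = 500: p = 2% gives 5.4, 10% gives 26.9, 20% gives 53.8.
- Group A only, N = 500 × 2/4 = 250: p = 2% gives 2.7, 10% gives 13.5, 20% gives 26.9.

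Group A is the relevant base for the single-dose TLC599 objective, because only Group A receives TLC599 as Injection 1. These are upper bounds: a patient who leaves before Week 24 adds nothing, and one who leaves before Week 52 adds less.

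**Do the rules force the exclusion?** The exclusion needs both a hard end to Injection 1 reporting at Week 24 and a ban on tables that cross periods.

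1. *Hard end at Week 24.* Section 11.2 gives an eligibility condition for each report and no dates. The 24 weeks come from a list of planned maximum durations, and Section 8.2 treats patients without Injection 2 in its own line, counting their 52 weeks from Injection 1. The lengths are also nominal. The Week 24 visit has a window of ±7 days, so Injection 2 may fall at Week 25; a strict 24-week cut would then leave 7 days unassigned even for patients who receive both injections. These are visit-planning figures and do not work as data cut-offs.
2. *Ban on cross-period tables.* Section 11.3.4.1 runs treatment-emergent events to the end-of-study or early-termination visit and displays adverse events by treatment group without naming a period. Sections 11.3.4.2 to 11.3.4.4 summarise laboratory values, vital signs and ECGs by time point. Section 11.3.4 summarises continuous safety data by visit, with change from the Injection 1 and/or Injection 2 baseline. A whole-study adverse-event table and Week 28 to 52 visit rows are natural readings of this text. The sentence about summaries within each period does not say that nothing else will be produced.

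Neither condition is established.

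**The case for a change.** The case for a change is that the sponsor plainly expects this group: Section 6.7 says that missing Injection 2 is not a deviation, and Section 11.3.1.1 tabulates the reasons. Yet no visible sentence says where the group's later safety data are summarised. The by-visit and adverse-event provisions sit under the within-period sentence of Section 11.3.4, and nothing says that they override it. A sentence or two would settle the matter, and settling it before unblinding avoids a choice made with results in view.

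The absence of an explicit assignment stands, as does the absence of an exact cut date. The risk of a choice made with results in view is small: Section 11.3 requires the SAP before database lock, and Section 7.7 allows overall unblinding only after lock. The supplied copy also lacks the text of Section 11.1.3 and the first Injection 2 criterion, and contains no separate SAP. Those absences cannot be counted as gaps in the plan, and a rule may already exist there.

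The obvious remedy also has a cost. Running the Injection 1 Period to Week 52 only for patients who miss Injection 2 would add longer, safety-selected follow-up to one side of the planned Group A comparison of Injection 1 with Injection 2. That comparison now has windows of about 24 and 28 weeks.

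**Conclusion.** No change to the plan is needed. The text is silent on a reporting convention, and the reading that would lose data is neither the only one nor the most natural one. No data go uncollected or unlisted, single-dose safety through Week 24 is reported for everyone given Injection 1, and no stated rule forces a wrong safety conclusion.

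What is at issue is where the last 28 of 52 weeks are tabulated for patients without Injection 2. For single-dose TLC599 this is at most 2.7 to 26.9 patient-years, assuming that 2% to 20% of about 250 Group A patients miss Injection 2. The conclusion assumes that the SAP sets the convention before lock, as Section 11.3 provides, and that adverse events are also tabulated over the whole study, as Section 11.3.4.1 is most naturally read.

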5. OBJECTIVES

5.1. Primary Objective

The primary objective is to evaluate the efficacy of a single IA dose of TLC599 in patients with OA of the knee.

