6.7. Patient Withdrawal from the Study

All patients will be advised that they are free to withdraw from participation in this study at any time, for any reason, and without prejudice. The investigator should make every reasonable attempt to keep patients in the study; however, patients must be withdrawn from the study if they withdraw consent to participate. Patients who do not receive Injection 2 do not need to be withdrawn and will be encouraged to continue in the study through 52 weeks of follow-up. If a patient does not receive Injection 2, it will not be considered a protocol deviation. Investigators must attempt to contact patients who fail to attend scheduled visits by telephone or other means to assess the possibility of an AE being the cause of withdrawal. Should this be the cause, the AE must be documented, reported, and followed as described in Section 9.2.

A participant should be withdrawn from the study if any of the following occurs:

- Pregnancy
- Significant study non-compliance
- Lost to follow-up
- A surgical procedure or IA drug administration in the index knee
- Lack of therapeutic effect that is intolerable or otherwise unacceptable to the patient
- If any clinical AE, laboratory abnormality, or other medical condition or situation occurs such that continued participation in the study would not be in the best interest of the participant
- The investigator or the Sponsor stops the study for any reason

If important restricted medication deviations occur, they should be discussed with the medical monitor before withdrawing the patient from the study.

The investigator should contact the medical monitor to discuss any non-compliance or safety concerns before withdrawing a patient from the study.

The reason for participant withdrawal from the study will be recorded on the eCRF. Patients who sign the ICF, are randomized, and receive study drug, and subsequently withdraw, or are withdrawn from the study, will not be replaced.

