11.3.3.1. Primary Analysis

The primary efficacy analysis and estimation of the primary estimand will be based on the FAS population, the mPP population, and the PP population.

The primary estimand is the difference in mean change from Baseline in WOMAC Pain score at Week 12 between TLC599 vs. Placebo (as defined in the Treatment Assignment Table in Section 7.2). The endpoint and intercurrent events for the primary estimand are defined as follows:

- Endpoint: Change from Baseline in WOMAC Pain score at Week 12
- Intercurrent Events:

An ANCOVA will be performed with treatment group as a fixed effect and Baseline WOMAC Pain score as a covariate. Multiple imputation will be used to impute missing intermittent and post-withdrawal WOMAC Pain scores considered to be missing at random. Post-withdrawal missing data due to lack of efficacy, AE, or surgical procedure/IA drug administration in the index knee will be assumed to be MNAR; all other missing and post-withdrawal data will be assumed to be MAR.

The ANCOVA model will be conducted on each imputation and the results will be combined using Rubin's rules in SAS PROC MIANALYZE.

The least-squares mean comparing TLC599 to Placebo along with the corresponding 95% confidence interval, will be used to estimate the treatment difference.

Sensitivity analyses will be conducted to estimate sensitivity estimators and to assess the robustness of efficacy results, including:

- A sensitivity analysis using a tipping point procedure to assess the robustness of the multiple imputation results.
- A mixed-effects model repeated measures (MMRM) approach will be used as a sensitivity analysis for the primary endpoint. Treatment group, study visit (as a categorical variable) and

site will be modeled as fixed effects, with a treatment-by-visit interaction and baseline WOMAC Pain score as a covariate. Patient will be included as a random effect. Prior to implementing the model, MNAR data due to intercurrent events will be imputed using BOCF and non-missing data affected by the use of intercurrent medications and procedures will be replaced using BOCF, as described for the primary analysis method. The MMRM will include both observed and BOCF imputed data.

If further sensitivity analysis on the primary endpoint is performed, it will be described in the SAP. Descriptive summaries (such as mean, standard error, first quartile, median, third quartile, minimum, and maximum) will also be provided for the primary endpoint.

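### The supportive Week 12 results in the mPP and PP sets depend on visits, events and a second injection that come after Week 12

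*Combined protocol and SAP*

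**What the plan says.** Section 5.1 sets the aim: "The primary objective is to evaluate the efficacy of a single IA dose of TLC599 in patients with OA of the knee". Section 11.1.1.1 reads it as change in WOMAC Pain at Week 12, Group A against Group C.

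Section 11.2 defines the sets. The FAS is everyone randomized who received Injection 1, and "The FAS population will be the primary population for efficacy analysis". The same section gives mPP and PP a supportive role for selected efficacy endpoints. For mPP, "for the mPP population, patients must have a valid WOMAC Pain assessment at Baseline, Week 12, and Week 24". For PP, "The PP Population includes all patients who receive 2 doses of study drug, have primary efficacy evaluation at Weeks 12, 24, and 36", and the scores at those weeks must be valid. Validity is tested at each required visit: "A valid assessment is within the analysis visit window and not excluded due to an intercurrent event".

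Section 11.3.3.1 then names all three sets for the Week 12 endpoint without ranking them: "The primary efficacy analysis and estimation of the primary estimand will be based on the FAS population, the mPP population, and the PP population".

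Section 6.7 says of the second injection: "If a patient does not receive Injection 2, it will not be considered a protocol deviation".

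**The concern.** A Week 12 outcome is settled at Week 12, but membership of the two adherence sets is decided at Week 24 (mPP) or Week 36 (PP). A patient who received Injection 1, kept to the protocol and gave a clean Week 12 score leaves the mPP set if the Week 24 score is missing, out of window or excluded for an intercurrent event. The same patient leaves the PP set for not receiving Injection 2, or for lacking a valid Week 36 score. The exclusion for important deviations is not limited to the time before Week 12 either.

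Some reasons for later loss are tied to outcome or treatment. Section 6.7 lists unacceptable lack of effect as a ground for withdrawal. Section 6.6.3 bars Injection 2 after adrenal insufficiency, which in a corticosteroid trial may differ by arm. Others have nothing to do with adherence: under Section 8.1, a patient kept away by COVID-19 restrictions cannot have Injection 2 outside the visit window.

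A per-protocol result is useful when it shows what non-adherence did to the full-set result. Here a gap between the FAS and mPP or PP at Week 12 mixes adherence up to Week 12 with selection after it.

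**Working it through.** **Timing.** Week 24 is 24 - 12 = 12 weeks after the endpoint, and Week 36 is 36 - 12 = 24 weeks after it. Injection 2 is given at Week 24. No adherence set in Section 11.2 stops at Week 12.

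**Inputs from the documents.** 500 patients at 2:1:1 gives 250, 125 and 125, so A against C is 250 against 125. WOMAC Pain is normalized to 0-4. The assumptions behind the 500 are not visible, so that figure cannot be reproduced; nothing here rests on it.

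**Assumed inputs.** True Week 12 difference -0.30 (mean change -0.9 in A, -0.6 in C, the same at Week 24), SD 0.9, Week 12 to Week 24 correlation 0.7. Loss after Week 12 follows logit(p) = a + b × (Week 24 change), where a higher change is worse pain. There were 2,000,000 simulated patients per arm. The estimate is the difference in mean Week 12 change among those retained. Example settings:

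| Setting | Lost A / C | Week 12 estimate |
|---|---|---|
| a = -1 in both, b = 1 | 16% / 20% | -0.282 |
| a = -0.5 in both, b = 1.5 | 20% / 26% | -0.263 |
| a = -2 (A), -1 (C), b = 1 | 7% / 20% | -0.238 |
| a = -2 (A), -0.8 (C), b = 1.5 | 7% / 22% | -0.205 |
| a = -1 (A), -2 (C), b = 1 | 16% / 9% | -0.335 |
| a = -0.5 (A), -1.5 (C), b = 1 | 23% / 14% | -0.345 |
| b = 0 (unrelated to pain), a = -1.4 in both | 20% / 20% | -0.301 |

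Across the settings tried, the ranges are about -0.26 to -0.28 (one loss model in both arms), about -0.20 to -0.24 (placebo more prone to leave) and about -0.34 (TLC599 more prone to leave).

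**Scale of the shift.** SE = 0.9 × sqrt(1/250 + 1/125) = 0.099. One loss model: shift 0.02 to 0.04, or 0.2 to 0.4 SE. Higher placebo loss: 0.06 to 0.10, or 0.6 to 1.0 SE. Higher TLC599 loss: 0.04 the other way, or 0.4 SE.

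**Second check, no true effect.** 4,000 trials of 250 against 125, SD 1, loss logistic in the Week 12 change with slope 1 per SD unless stated. A positive bias is against TLC599.

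- 20% lost in both arms, same mechanism: bias 0.00 SD, nominal rejection 5.4%.
- 10% (A) against 20% (C): +0.08 SD, 11%. Reversed: -0.08 SD, 11%.
- 15% against 30%: +0.12 SD, 17%. Reversed: -0.12 SD, 17%.
- 20% in both, pain-related in A only: -0.17 SD, 29%. In C only: +0.175 SD, 32%.
- All treated patients analysed: 4.6% to 5.4% throughout.

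**Precision.** Discarding 20% of Week 12 scores multiplies the SE by 1/sqrt(0.8) = 1.12. A standardized effect with 90% power in 250 against 125 is (1.96 + 1.28) × sqrt(1/250 + 1/125) = 0.355. With 200 against 100 its power falls to 83%.

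**The case against.** The strongest reply is that none of this touches the lead analysis. A reader of Section 11.3.3.1 might infer that the primary single-dose conclusion itself turns on Weeks 24 and 36. The documents do not support that: Section 11.2 makes the FAS primary for efficacy and mPP and PP supportive, and no later visit is needed to be in the FAS. This stands, and it limits the point to the supportive results. What remains is that Section 11.3.3.1 lists the three sets under the primary analysis without that ranking, so the two sections should be reconciled.

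Three further replies have force:

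- Section 11.3.1.1 tabulates withdrawal reasons and timing and the reasons for not receiving Injection 2, and Section 11.2 fixes membership at blinded review. Attrition after Week 12 will therefore be visible by arm, and it would be too strong to say that a disagreement with the FAS could not be investigated. But a table of attrition does not remove its effect from the estimate.
- A reader might see a contradiction between Section 6.7 and the PP definition. There is none: receiving two doses and having no important deviation are separate criteria. The point is only that a two-dose criterion does not suit a single-dose Week 12 endpoint.
- Recurrent pain need not invalidate a Week 24 score. Rescue acetaminophen and, within limits, episodic use of certain opioids are permitted, and patients without Injection 2 are encouraged to stay. The list of intercurrent events is not visible and the analysis visit window is not defined in the visible text, so the amount of loss cannot be estimated.

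One could also defend a single common set across endpoints from Week 12 to Week 24, since it keeps the patients the same. That is a real convenience, but the cost falls on the earliest and most important endpoint.

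**Conclusion.** The point holds for the mPP and PP results at Week 12, and only for them. Both sets drop patients with valid Week 12 scores because of events 12 to 24 weeks later. The plan's own missing-data rule treats withdrawal for lack of efficacy or adverse events as not at random (Section 11.3.3.1), so such loss cannot be presumed harmless.

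Neither direction nor size can be known from the documents. With one loss model in both arms the shift is below half a standard error. It approaches one standard error only if placebo patients are assumed markedly more prone to leave, and it reverses if TLC599 patients are. A reader might infer that these sets err on the cautious side; the working does not support that. The nominal rejection rates describe the supportive sets and are not the trial's type I error, because the FAS is the primary efficacy population.

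The difference, SD, correlation and loss models are all assumptions. The model also has no average waning between Weeks 12 and 24. This is a worthwhile correction to a supportive analysis and does not threaten the primary test.

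**What to change.** Amend Section 11.2 and carry the change into the SAP before the blinded data review.

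1. Define the supportive adherence set by endpoint week. For endpoints through Week 24: Injection 1 received, valid WOMAC Pain at Baseline and at the week analysed, and no important deviation affecting efficacy up to that week. The Week 12 set then uses only data through Week 12, and the Week 16 and 20 sets no longer need a Week 24 score.
2. For Weeks 36 and 52, also require Injection 2 and a valid score at the week analysed. Reusing the current PP set unchanged at Week 52 would not do this, because it asks for Week 36 and not Week 52.
3. Reword Section 11.3.3.1 so that the FAS is the sole basis of the primary test and the adherence sets are supportive, in line with Section 11.2.

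The cost is a few sentences and extra population flags, with no new data. Set sizes will differ between endpoints, so each table should show its own counts. A Week 12 adherence set is still selected after randomization and should be read as supportive; the change removes only the selection that occurs after the endpoint.
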